Study Title

Hepatic Vein Flow During Orthotopic Liver Transplantation as Predictive Factor for Postoperative Graft Function

NCT03814031

03/18/2019

Study Protocol

Patient Cohort

Inclusion criteria are adult patients undergoing the orthotopic liver transplantation (OLT) piggyback technique with transesophageal echocardiography (TEE)-measured hepatic vein (HV) flow. Exclusion criteria are patient refusal to participate in the study, absolute TEE contraindication, inability to acquire appropriate images for HV flow measurement, or unavailability of a cardiac trained anesthesiologist.

All patients receive general anesthesia with endotracheal intubation, standard American Society of Anesthesiologists monitoring, arterial blood pressure monitoring, central venous pressure monitoring, pulmonary artery pressure monitoring, and comprehensive TEE examination with designated protocol. Intraoperative anesthetics, mechanical ventilation, vasopressor, inotropic, and fluid/transfusion management are performed based on department protocol such as to maintain mean arterial pressure > 65 mmHg, tidal volume 6-8 ml/ideal body weight (kg), positive end-expiratory pressure at 5-7 cmH₂O.

Data Collection

TEE images are intraoperatively collected by National Board of Echocardiography-certified advanced perioperative echocardiographers using an iE33 echocardiographic machine with an X7 TEE probe (Philips Medical Systems, Andover, MA), and stored in Syngo Workflow (Siemens Medical Solution, Malvern, PA, USA). Timing for acquiring TEE modified transgastric HV view is in neohepatic phase before fascia closure. To obtain HV flow, the Pulse Wave Doppler (PWD) sample volume is set in the graft HV just distal to IVC-graft anastomosis where an acceptable flow envelope is obtained.

Echocardiography Parameters

Three investigators (A, B, and C), who was also National Board of Echocardiography (NBE)-certified advanced perioperative echocardiographers, measures hepatic vein flow (HVF) in systole and diastole independently using TEE images which are acquired by a single cardiac anesthesiologist (advanced TEE boarded). We calculate HVF as follows: HVF (L/min) = HV area (cm²) x HV max velocity (cm/s) in systole and diastole x 60/1000, where HV area (cm²) = square of HV radius (cm) x 3.14, and HV max velocity (cm/s) is measured by TEE PWD with sample volume selected in the HV, where diameter of HV is measured as well. Efforts are made to align PWD and HV. We define HV flow index (HVF_i) as HVF/donor liver weight (kg). We adjust HVF with graft weight because it is more common to assess graft flow with graft size recently. To minimize selection bias, all the investigators are blinded to the hypothesis of the study.

Outcomes

Primary outcome is early allograft dysfunction (EAD), which is defined by the presence of one or more of the following: total bilirubin (t-bil) ≥ 10 mg/dL (171 μ mol/L) or, INR ≥ 1.6 on day 7, and ALT/AST $> 2,000$ IU/L within the first 7 days. Secondary outcome is acute rejection within 6 to 8 weeks post-transplant), prolonged (> 7 days) time to normalize total bilirubin (TIME t-bil), prolonged (>7 days) time to normalize INR (TIME inr), and prolonged (>7 days) time to normalize platelet count (TIME plt).

Statistical Analysis

For continuous variables, the normality test is performed using the Kolmogorov-Smirnov test. Continuous variables with normal distribution are displayed as mean \pm standard deviation, while those with non-normal distribution are displayed as median and interquartile range. Categorical variables are presented as proportions and absolute numbers. The differences between the two groups are investigated using unpaired and paired Student t tests or the Mann-Whitney U test. Chi-square test or Fisher's exact test is used for categorical variables. HVFi (systolic and diastolic) are compared in groups of EAD vs. no EAD, acute rejection vs. no acute rejection, no prolonged INR, t-bil, low plt vs. no prolonged INR, t-bil, low plt.

Intra-rater and inter-rater reliability analyses of HVFi are performed using intraclass correlation coefficient (ICC). We randomly pick up 30 images and obtain consistency ICC for inter-observer variability using all three investigators (A, B, and C), and absolute-agreement ICC for intra-observer variability using investigator C, who measure all images twice with an interval between 6 and 8 weeks. For inter-observer variability, 3 investigators post-hoc determine HV diameter, the peak systolic and peak diastolic flow based on the pulse-wave Doppler signal. All statistical analyses are performed using R (The R Foundation for Statistical Computing, Vienna, Austria. ver 4.0.2). P values of less than 0.05 are considered statistically significant.

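### Hepatic vein flow readers are blinded to the hypothesis but not stated to be masked to outcome, and the reading used in the EAD comparison is neither dated nor assigned to a reader or round

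*Combined protocol and SAP*

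**What the plan says.** All references are to the combined protocol and SAP.

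- **Masking.** Echocardiography Parameters gives one rule: "To minimize selection bias, all the investigators are blinded to the hypothesis of the study". The same section has three investigators (A, B and C) measure flow independently of one another.
- **Images.** Under Data Collection, the echocardiographic images are taken during surgery, before fascia closure, and "stored in Syngo Workflow".
- **Measurement.** Flow is vein area times peak velocity times a constant, with area computed as "square of HV radius (cm) x 3.14". HVFi is flow divided by donor liver weight.
- **Outcomes.** EAD uses bilirubin and INR on day 7 and a transaminase criterion of more than 2,000 "IU/L within the first 7 days". A secondary outcome is "acute rejection within 6 to 8 weeks post-transplant".
- **Main comparison.** Under Statistical Analysis, "HVFi (systolic and diastolic) are compared in groups of EAD vs. no EAD".
- **Reliability.** The same section bases the intra-observer ICC on one reader, C, "who measure all images twice with an interval between 6 and 8 weeks". The readings that serve the agreement between observers are described separately: "3 investigators post-hoc determine HV diameter, the peak systolic and peak diastolic flow".

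**The concern.** HVFi is the predictor in the primary comparison, and it is the side of that comparison that depends on a reader's judgement. EAD rests on laboratory values. HVFi rests on where a reader places the calipers and which velocity peak is taken.

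Blinding to the hypothesis and masking to outcome do different things. The first reduces a reader's expectation about which direction a result should go. The second removes the knowledge of which patients did badly. The plan states only the first. It also gives selection bias as the aim, whereas masking of readers guards against measurement bias.

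Errors that are random, or the same proportion in every patient, would mostly add noise or cancel between groups. Errors linked to a known outcome would not. They could create a difference between EAD and no EAD, or hide one.

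**Working it through.** The plan states no figure on this point, so there is none to reproduce. The check sets the passages side by side, then uses dates and the plan's own formula.

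**1. Is outcome masking stated anywhere?** No. The hypothesis-blinding sentence is the only masking text in the document. Independent measurement means that the readers work apart from one another; it does not say that they work apart from outcome data.

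**2. Could acquisition be affected?** No. Images are acquired during the transplant operation, before any component of EAD can be known. Only the later measurement of stored images is exposed.

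**3. When is the reading for the main analysis made?** This is not stated. EAD is settled by day 7. Images exist from day 0 and can be read at any time after that. A reading before day 7 and a reading after it are both compatible with the text.

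**4. Whose reading is it?** This is not stated either. A, B and C all measure flow, and C measures twice. The plan does not say whether the EAD comparison uses one reader, an average, or C's first or second round.

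**5. What do the stated intervals add?** C's two readings are 6 to 8 weeks apart, which is 6 × 7 = 42 to 8 × 7 = 56 days. With the earliest possible first reading on day 0:

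- 6-week interval: second reading on day 42, and 42 − 7 = 35 days after EAD is settled
- 8-week interval: second reading on day 56, and 56 − 7 = 49 days after EAD is settled

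A later first reading lengthens the lag. So C's second reading always follows EAD status. The plan describes that reading only for the intra-observer ICC, however, so this shows nothing about the values in the main comparison. The dates that matter there are the missing ones in step 3.

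**6. How does a reading shift pass into HVFi?** With diameter d and peak velocity v,

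HVFi = 3.14 × (d/2)² × v × (60/1000) / donor liver weight.

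If a reader shifts d by a proportion a and v by a proportion b, HVFi is multiplied by (1 + a)² × (1 + b). With b = 0:

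| Shift in diameter | Change in HVFi |
|---|---|
| +2% | 1.02² − 1 = +4.04% |
| +5% | 1.05² − 1 = +10.25% |
| +10% | 1.10² − 1 = +21% |
| −2% | 0.98² − 1 = −3.96% |
| −5% | 0.95² − 1 = −9.75% |
| −10% | 0.90² − 1 = −19% |

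The shifts are illustrative; the documents give no reading error. The table shows how the formula magnifies any diameter error, whatever its cause. It does not measure bias.

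**The case against.** **Silence is not evidence of unmasked reading.** This stands. The protocol is very short, and nothing in it says that readers had laboratory results or the clinical record. The point is that the plan does not exclude outcome-aware reading, not that it took place.

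**The late readings are for reliability only.** This also stands. A reader might infer from the 35-day minimum in the working that outcome-aware values enter the EAD comparison. The documents do not support that: C's repeat reading is described for the intra-observer ICC, and the post-hoc readings are introduced for inter-observer variability. A delay between repeat readings is sensible in itself, since it limits recall. Nor need rejection status be settled at C's second reading, because day 42 is only the start of the 6 to 8 week range.

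**Hypothesis blinding already protects the comparison.** This stands in part. Differential bias needs a reader who both knows the outcome and leans in a direction linked to it, and hypothesis blinding acts on the second condition. It leaves the first untouched. Experienced echocardiographers measuring graft vein flow could plausibly guess the question.

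**The percentages do not show harm.** Agreed; they are geometry. If the three readers' values were averaged, which the plan does not state, a shift by one reader would be diluted to about a third.

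**The reliability analysis would reveal a problem.** This does not stand. Readers who share outcome knowledge can agree closely while shifting in the same direction, and the inter-observer ICC is a consistency ICC, which ignores constant offsets between readers.

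**Conclusion.** The point holds in a limited form, as a cheap improvement to the plan. The stated safeguard does not keep readers of a manually measured predictor from knowing the outcome. The reading used in the primary comparison has no stated date, reader or round, so differential measurement bias remains possible.

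No size of bias and no false-positive rate is claimed. Either would need the sample size, the EAD share, the spread of HVFi, the reading error, and how consistently any shift followed outcome. The documents give none of these.

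The conclusion assumes that the document contains the whole masking arrangement. If a separate reading procedure already masks outcomes, the remedy reduces to stating it.

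**What to change.** Keep hypothesis blinding and add to Echocardiography Parameters:

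*To minimize measurement bias, stored images are de-identified and read in random order by investigators masked to EAD, rejection, laboratory values and clinical course. The HVFi values for the main analysis come from a reader and reading round named in advance, and are locked before linkage to outcomes.*

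The cost before reading starts is two sentences of text, relabelling and shuffling of the stored studies, a dated lock, and a linkage key held by existing staff outside the reading team. No extra patient, image or procedure is needed.

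If the readings are already complete, report who was masked to what, when the readings were made, and which reader and round supplied the analysed values. This point does not require a full masked re-read.

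### Plain Kolmogorov-Smirnov is a weak normality check for HVFi: with mean and SD estimated from the sample it misses mild-to-moderate skew at up to about 100 patients, so the HVFi test should be named in advance

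*Combined protocol and SAP*

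**What the plan says.** The Statistical Analysis section opens with the normality rule: "For continuous variables, the normality test is performed using the Kolmogorov-Smirnov test". Variables judged normal are shown as mean ± SD, "while those with non-normal distribution are displayed as median and interquartile range". The next relevant sentence covers testing: "The differences between the two groups are investigated using unpaired and paired Student t tests or the Mann-Whitney U test". No rule for choosing between these tests is written out; the reader has to infer it from the normality sentence.

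The variable that matters most is HVFi: "HVFi (systolic and diastolic) are compared in groups of EAD vs. no EAD", and likewise for the secondary outcomes. The Echocardiography Parameters section defines it. Flow is "HVF (L/min) = HV area (cm²) x HV max velocity (cm/s) in systole and diastole x 60/1000", with "HV area (cm²) = square of HV radius (cm) x 3.14", and the index divides this flow by graft weight in kilograms.

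The section does not say where the reference mean and SD come from, whether the Lilliefors correction applies, or whether the check is run on the pooled sample or per group. It names R but no function. The documents give no sample size, EAD rate, expected HVFi distribution or direction of effect.

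**The concern.** The ordinary Kolmogorov-Smirnov critical value is valid only when the mean and SD of the reference normal curve are fixed beforehand. The plan fixes neither, so they must come from the sample. The fitted curve then lies closer to the data than the critical value allows for, and the test seldom rejects.

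HVFi is the variable most exposed. Radius enters squared, is multiplied by velocity, and the result is divided by weight. Quantities built this way from positive measurements tend to be skewed to the right. If the check misses that skew, HVFi is summarised by a mean and SD that describe it poorly, and the primary comparison probably goes to a t test on the raw scale when a rank or log-scale test would often do better. The choice of primary test would then rest on an unreliable pre-test of the same data.

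**Working it through.** The plan states no figure to reproduce, so the check is by simulation. **Inputs from the documents:** the test named, the HVFi formula, the two candidate tests and the 0.05 threshold. **Assumptions not in the documents:** log-normal HVFi, total N of 30 to 200, 25% of patients with EAD, two-sided testing.

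**1. Plausible skew.** With HVFi proportional to r²·v/w and independent components, log-SD = √[4·ln(1+CVr²) + ln(1+CVv²) + ln(1+CVw²)].
- CVs of 15%, 25% and 20% (radius, velocity, weight): √(0.0890 + 0.0606 + 0.0392) = √0.1888 = 0.43.
- CVs of 20%, 30% and 20%: √(0.1569 + 0.0862 + 0.0392) = √0.2823 = 0.53.

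These imply skewness of about 1.5 to 1.9. If larger grafts have larger veins (assumed log-scale correlation 0.5), log-SD falls to 0.36–0.45.

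**2. Behaviour on normal data.** With sample mean and SD plugged in, the nominal 5% critical value is 0.242 at N=30, where the correct one is 0.159; at N=100 the values are 0.134 and 0.089. The ratio is about 1.5 in both cases. Rejection under normality is about 0.01–0.02%, not 5%.

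**3. Behaviour on log-normal data with log-SD 0.5.**

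| N | Plain KS rejects | Shapiro-Wilk rejects |
|---|---|---|
| 30 | about 4% | about 74% |
| 60 | about 18% | about 97% |
| 100 | about 45% | about 99.9% |

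The Lilliefors-corrected version rejects 71% at N=50 and 95% at N=100. The plain test does detect stronger skew or larger samples: 81% at N=50 with log-SD 1.0, about 85–87% at N=100 with log-SD 0.7, and 89% at N=200 with log-SD 0.5.

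**4. Power.** The check is run on the pooled sample and assumed to choose between t test and Mann-Whitney. Log-SD is 0.5 and the group difference is 0.5 log-SD.

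| Groups | Smaller group's HVFi | Gated choice | Mann-Whitney | t on log HVFi |
|---|---|---|---|---|
| 15 vs 45 | lower | 31–32% | 36% | 38% |
| 15 vs 45 | higher | 37–38% | 35–36% | 37–38% |
| 25 vs 75 | lower | 52% | 55% | 58% |
| 25 vs 75 | higher | 54–55% | 55% | 57% |

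When the smaller group has lower HVFi, the loss is about 3 to 7 points, depending on N and on the comparator. In the other direction it is about 0 to 3 points. With effects set for about 80% power and the smaller group lower, the loss against Mann-Whitney is 1–14 points at N=30 and 0–3 points at N=100. The extreme is N=30 with log-SD 1.0 and the check run per group: 50.5% against 75.6%, a loss of 25 points.

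**5. Type I error.** The gated procedure stays at 4.3–5.1%.

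**6. Summary measure.** For a median of 1 and log-SD 0.5, the mean is 1.133 and the SD 0.604, so mean minus 2 SD = 1.133 − 1.208 = −0.07, an impossible flow. At log-SD 0.44 the same quantity is +0.08. This is a matter of presentation and arises only near the upper end of the assumed skew.

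**The case against.** The strongest reply is that the defect is partly presumed. The text does not exclude a Lilliefors correction, and with it the test rejects 4.6–5.3% of normal samples and detects log-SD 0.5 well. The text also links the normality result explicitly only to the summary measure; the link to the choice of test is inferred. Both observations stand, and they limit the claim. They do not remove it, because the test as named carries no correction, and two analysts following the section could run different primary tests on identical data.

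A reader might infer that the check can hardly ever reject, that a skewed HVFi would routinely be treated as normal, or that the primary comparison necessarily loses power. The documents support none of these. Detection depends on sample size and skew, neither of which is given, and strong skew is usually caught from about 50–100 patients. The power loss depends on direction, which is also not stated, and nearly vanishes when the smaller group has the higher values. Simulating log-normal data also favours the log-scale test by construction; against Mann-Whitney, already in the plan, the loss with the smaller group lower is about 3–5 points.

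**Conclusion.** The point holds in limited form. Run as named, with mean and SD from the sample, the check does its stated job badly: near-zero rejection under normality, and mild-to-moderate skew mostly missed at up to about 100 patients. The result under normality does not depend on how HVFi is distributed. The consequences for HVFi do: they rest on an assumed log-normal shape, log-SD near 0.5, 60–100 patients, EAD as the smaller group, and the inferred link from the normality check to the test. Under those assumptions the cost is a poor summary measure and a power loss that ranges from none to several points. Validity is not threatened. The plan should be changed because the remedy is cheap and the choice of primary test should not hang on an unreliable pre-test.

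**What to change.** In the Statistical Analysis section:

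- Do not let a normality pre-test choose the primary HVFi comparison. Name one test in advance for systolic and diastolic HVFi: either a t test on log HVFi, reported as a geometric mean ratio with 95% CI, or Mann-Whitney. Keep the other as a sensitivity analysis.
- Summarise HVFi as median and IQR regardless of any normality result.
- If a normality check is kept for other variables, replace plain Kolmogorov-Smirnov with Shapiro-Wilk or the Lilliefors-corrected version, and say whether it is run pooled or per group.

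The cost is SAP wording only, with no extra patients or data. The one small downside is that, on the log scale, the effect is reported as a ratio instead of a difference.

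### The title asks whether hepatic vein flow predicts graft function, but the plan offers only two-group tests at p<0.05 for two co-equal indices, with no AUC or other effect estimate with a confidence interval

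*Combined protocol and SAP*

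**What the plan says.** The title sets the question: "Hepatic Vein Flow During Orthotopic Liver Transplantation as Predictive Factor for Postoperative Graft Function". Under Outcomes, the primary outcome is binary: "Primary outcome is early allograft dysfunction (EAD), which is defined by the presence of one or more of the following". Under Echocardiography Parameters, flow is calculated separately for systole and diastole from one vein area, and each value is then indexed: "We define HV flow index (HVF_i) as HVF/donor liver weight (kg"). There are therefore two candidate predictors, and they share the vein area and the graft weight.

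The Statistical Analysis section links these predictors to the outcome in one sentence: "HVFi (systolic and diastolic) are compared in groups of EAD vs. no EAD, acute rejection vs. no acute rejection". The method is also given in one sentence: "The differences between the two groups are investigated using unpaired and paired Student t tests or the Mann-Whitney U test". The decision rule is "P values of less than 0.05 are considered statistically significant", with no statement of sidedness. The only other inferential statistic is the intraclass correlation coefficient, which concerns rater reliability. The section contains no ROC analysis, regression, odds ratio or confidence interval for an effect, and it does not rank the two indices.

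**The concern.** A test of whether mean or typical HVFi differs between patients with and without EAD addresses association. A predictive factor has to be judged on how well it separates the two groups and how precisely that separation is known. The p-value answers neither question alone, because it depends on the number of patients as well as on discrimination. The same p can go with quite different predictive ability, and the same predictive ability can come out significant or not according to enrolment.

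Because the two indices have equal standing, a positive finding on either could be presented as the result for the primary outcome. Someone following the plan exactly could conclude that hepatic vein flow predicts EAD from one p-value below 0.05 on whichever index gave it, with no planned statement of how well it predicts.

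**Working it through.** **Is there a design figure to reproduce?** No. The document gives no sample size, EAD rate, effect size or power. The central point is about what is specified and needs no arithmetic. The calculations below only illustrate its size.

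**Inputs.** From the document: threshold 0.05, two indices, one binary primary outcome. Assumed: EAD/no EAD of 12/38, 25/75 and 50/150; two-sided tests; HVFi normal with equal variance in both groups; correlation between the two test statistics from 0 to 0.9.

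**Step 1. Same p, different discrimination.** At a given two-sided p, the standardised difference is d = t(1−p/2, n−2) × √(1/n1 + 1/n0), and AUC = Φ(d/√2).

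| EAD/no EAD | √(1/n1+1/n0) | p=0.05: t, d, AUC | p=0.01: t, d, AUC |
|---|---|---|---|
| 12/38 | 0.331 | 2.011, 0.666, 0.681 | 2.682, 0.888, 0.735 |
| 25/75 | 0.231 | 1.984, 0.458, 0.627 | 2.627, 0.607, 0.666 |
| 50/150 | 0.163 | 1.972, 0.322, 0.590 | 2.601, 0.425, 0.618 |

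Varying the EAD rate from 15% to 35% moves the AUC at p=0.01 from 0.77 to 0.71 (n=50), 0.70 to 0.65 (n=100) and 0.64 to 0.61 (n=200).

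**Step 2. Same discrimination, different p.** Fix the true AUC at 0.65, so d = √2 × Φ⁻¹(0.65) = 0.545. The noncentrality parameter is d/√(1/n1 + 1/n0), which is 1.65, 2.36 and 3.34 for the three sizes. From the noncentral t distribution, the chance of p<0.05 is 36%, 65% and 91%. The average half-width of a DeLong 95% CI for the AUC at these sizes is 0.18, 0.12 and 0.09 (4,000 simulations).

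**Step 3. Two indices, neither primary.** With no true association, the chance that at least one of two tests has |z|>1.96 is 1 − 0.95² = 0.0975 if they are independent. With a bivariate normal distribution it is 0.091 at correlation 0.5, 0.078 at 0.8 and 0.070 at 0.9. Because the indices share vein area and graft weight, a positive correlation is likely and the lower part of the range is more plausible. With one index named primary, the figure for the primary analysis is 0.05.

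**Step 4. What each planned test already contains.** For the Mann-Whitney test, U/(n1 × n0) is the empirical AUC. If that branch is taken, discrimination is computed in all but name, and what is missing is the instruction to report it with an interval. The t test produces no such quantity.

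**The case against.** The best reply is that the information is nearly there. On the Mann-Whitney branch, a reader given the exact p-value, the group sizes and the direction can work back to the AUC. In a simulation with lognormal data (sigma 0.5) and a true AUC of 0.65, p to three decimals recovered it with a mean error of 0.005, 0.003 and 0.001 at 12/38, 25/75 and 50/150. This stands as far as it goes. A reader might infer that the plan would leave discrimination unknowable, and the documents do not support that. But the recovery needs an exact p, which the plan does not promise; a bare statement of p<0.05 would not allow it. Nor does it settle which index the conclusion rests on.

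Second, the prediction aim rests on the title alone. The body states no predictive objective, cut-off or intended use, and predictive factor can loosely mean associated factor. This is fair. A reader might infer that the plan commits itself to declaring prediction from p<0.05; it does not say so, it only leaves that route open. Even on the association reading, an effect estimate with an interval would be needed.

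Third, a reader might take the point to be that the tests lack covariate adjustment. Dividing flow by graft weight defines the index and is not such adjustment. But the title does not claim an independent association, so the documents do not make an adjusted model necessary.

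Fourth, the false-positive inflation is modest at the correlations that are plausible here. That is accepted; it is the smaller part of the point.

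**Conclusion.** The point holds as a gap in pre-specification and reporting, and it should be fixed. The planned comparison is valid as a test of association, but it does not answer the title's question. The plan asks for no AUC or other effect estimate with a confidence interval, and it does not say which of two indices carries the primary result.

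Under the assumptions above, p=0.01 can mean an AUC anywhere from about 0.74 down to 0.62 across the three sizes, and a true AUC of 0.65 would reach p<0.05 between 36% and 91% of the time. The chance of at least one false positive for EAD is 7.0% to 9.8%, probably towards the lower end. These sizes depend on assumed group numbers, EAD rates, correlations and two-sided testing, none of which the document states. The absence of the estimate, the interval and the primary index does not depend on them.

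**What to change.** Before analysis, add to the Statistical Analysis section:

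- Name one index, systolic or diastolic HVFi, as the primary predictor of EAD and the other as secondary.
- Report the AUC with a 95% CI for each index, whichever group test is used. A logistic odds ratio per SD of HVFi with its 95% CI is an optional addition.
- Keep the t or Mann-Whitney tests as supporting analyses.
- Base any statement that hepatic vein flow predicts EAD on the primary index's AUC and its interval, not on the group p-value.

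The cost is a few sentences of wording and a few lines of R on data the plan already uses. The drawback for the sponsor is that an AUC with its interval may look less favourable than a p-value.

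### Inter-observer reliability of HVFi is planned only as a consistency ICC, so no planned output would show a systematic difference between readers A, B and C

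*Combined protocol and SAP*

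**What the plan says.** The last paragraph of Statistical Analysis names one reliability method: "Intra-rater and inter-rater reliability analyses of HVFi are performed using intraclass correlation coefficient (ICC"). The sample is set by "We randomly pick up 30 images". The two forms of ICC are then assigned as "obtain consistency ICC for inter-observer variability using all three investigators (A, B, and C), and absolute-agreement ICC for intra-observer variability using investigator C". Absolute agreement is therefore assessed only for C's first reading against C's second.

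The same paragraph says what is re-read for the between-reader part: "3 investigators post-hoc determine HV diameter, the peak systolic and peak diastolic flow based on the pulse-wave Doppler signal". Under Echocardiography Parameters, the vein area is computed as "square of HV radius (cm) x 3.14", and flow is area times peak velocity, divided by donor liver weight to give HVFi.

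The plan specifies no between-reader absolute-agreement ICC, mean reader difference, limits of agreement or per-reader summary. It does not say whether the ICCs are for single or averaged measurements, or whose readings enter the outcome comparisons.

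**The concern.** Two questions can be asked of three readers: do they rank patients alike, and do they obtain the same values? A consistency ICC answers the first. It can be high when one reader's values are uniformly larger than another's.

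A systematic difference is plausible here, although nothing in the documents shows that one exists. Each reader measures the vein diameter afresh, and the radius is squared, so a small proportional bias in diameter is roughly doubled in HVFi. If such a bias exists, someone reading the report would take the single coefficient as agreement and could not tell that it excludes the reader difference. What is at stake is the interpretation of a supporting reliability result, not the validity of the main comparison.

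**Working it through.** **Inputs from the documents.** 30 images; 3 readers; consistency ICC between readers; absolute agreement for reader C only; area proportional to radius squared. The plan states no ICC value, variance or reader offset, so there is no figure to reproduce.

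**Formulas.** From a two-way layout of *n* images by *k* readers, with mean squares for images (MSR), readers (MSC) and error (MSE), single-measure forms:

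- Consistency: (MSR − MSE) / [MSR + (k − 1)MSE]
- Absolute agreement: (MSR − MSE) / [MSR + (k − 1)MSE + (k/n)(MSC − MSE)]

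MSC does not appear in the consistency form. With *n* = 30 and *k* = 3, the extra term in the agreement form is (3/30)(MSC − MSE).

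**Constant offset.** Set the between-patient variance to 1 and shift one reader by *b* between-patient SDs. The reader variance is then b²/3. Take an assumed consistency ICC of 0.90, so the error variance is 1/0.90 − 1 = 0.111:

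- *b* = 0: agreement = 1/1.111 = 0.90
- *b* = 0.5: agreement = 1/(1.111 + 0.083) = 0.837
- *b* = 1: agreement = 1/(1.111 + 0.333) = 0.692

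Consistency is 0.90 in all three cases.

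**Proportional offset, the form a diameter bias would take.** A diameter 5% high multiplies flow by 1.05² = 1.1025; 10% high multiplies it by 1.10² = 1.21. The simulation used 20,000 data sets per setting, raw-scale HVFi, and assumed log-scale variances of 0.16 between patients and 0.04 or 0.0225 residual. Mean single-measure ICCs:

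| Diameter bias of the readers | Consistency / agreement, residual 0.04 | Consistency / agreement, residual 0.0225 |
|---|---|---|
| none | 0.768 / 0.768 | 0.856 / 0.856 |
| one reader +5% | 0.766 / 0.754 | 0.853 / 0.838 |
| one reader +10% | 0.760 / 0.717 | 0.845 / 0.791 |
| −5%, 0, +5% | 0.762 / 0.727 | 0.847 / 0.804 |
| −10%, 0, +10% | 0.740 / 0.626 | 0.824 / 0.684 |

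From the first row to the last, consistency falls by about 0.03 (0.768 − 0.740 = 0.028; 0.856 − 0.824 = 0.032). Agreement falls by 0.14 to 0.17 (0.768 − 0.626 = 0.142; 0.856 − 0.684 = 0.172). A fall of 0.03 could not be recognised in one sample: the central 95% range of the consistency ICC is about 0.60–0.88 or 0.74–0.93 for the two residual variances.

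**Would reader differences show the bias?** With 30 images, the 95% CI for a paired mean difference has a half-width of about 8–13% of mean HVFi. For the biased or most different pair, and for the two residual variances, it excludes zero in:

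- 39% / 62% of data sets when one reader is +5%
- 90% / 99% when one reader is +10%
- 93% / 99.5% at −5%, 0, +5%
- 100% at −10%, 0, +10%

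**The case against.** The plan uses both ICC terms, which suggests a deliberate choice, and consistency suits the stated use of HVFi. HVFi is only compared between outcome groups, and no cut-off or absolute target is planned. If one reader supplies every value, or the three are averaged for every patient, a constant offset cancels from the group difference. For a single reader, a proportional offset rescales the difference and its standard error together. Reader bias would reach the main comparison only if different readers supplied different patients' values, and the plan does not say whose readings are used. This stands, and it is why the point is confined to the reliability result.

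The size is wholly assumed. If averages of three readings were meant, the gaps are about half as large or less: about 0.006 for one reader +5%, about 0.02 for one reader +10% or for −5%, 0, +5%, and 0.06–0.07 for −10%, 0, +10%. A single-measure gap above 0.1 appears here only when two readers are 20 percentage points apart in diameter, and all the readers are board-certified and read the same stored images. This also stands.

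Statistical Analysis does mention paired t tests, but for two groups. The HVFi comparisons it then lists are between outcome groups, and there are three readers. It does not plan a reader comparison. Nor can the absolute-agreement ICC for C against C show a difference from A or B.

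**Conclusion.** The point holds as an inexpensive improvement. Between readers the plan specifies consistency only, and no planned output would show a systematic difference among A, B and C. If there is none, the two forms agree in expectation and nothing is lost. If there is one, the reported ICC overstates absolute agreement. Under the assumed variances and single-measure ICCs, the overstatement averages 0.01–0.02 for one reader +5%, 0.04–0.05 for one reader +10%, 0.03–0.04 for −5%, 0, +5%, and 0.11–0.14 for −10%, 0, +10%. At 5% the gap is small beside sampling error. The true size cannot be found from the documents, and the EAD comparison is not invalidated.

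**What to change.** On the same 30 images, for systolic and diastolic HVFi separately, also report the single-measure absolute-agreement ICC with its 95% CI, and the mean differences A−B, A−C and B−C with 95% CIs. The consistency ICC can stay beside them. State that single-measure ICCs are meant. Because a diameter bias acts proportionally, the differences could also be given as ratios from log HVFi. In the illustration this is slightly more sensitive for one reader +5%, excluding no difference in about 44% and 68% of data sets against 39% and 62% on the raw scale.

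The cost is one argument in the R call and a three-row table for each of systole and diastole, with no new images or readings. There are two downsides:

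- The absolute-agreement ICC will usually be lower if readers differ, and its CI can be wide because the reader variance rests on three readers (2 degrees of freedom). With residual variance 0.04, the median 95% CI is 0.55–0.86 at −5%, 0, +5% and 0.30–0.82 at −10%, 0, +10%, against 0.62–0.87 and 0.59–0.86 for consistency.
- The difference table does not depend on that variance, but with 30 images it can miss a small bias in one reader.
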